9.2 Subject Accountability

The number and percent of subjects who were enrolled into the OLE study, received IP, completed IP, discontinued IP and reasons for discontinuing during the OLE study, completed the OLE study, and discontinued the OLE study and reasons for discontinuing will be summarized by the randomized treatment group in parent study and overall.

OLE enrollment by region, country and investigator and, key study dates for the first subject enrolled, last subject enrolled and last subject's end of study will be presented.

9.3 Important Protocol Deviations

Important Protocol Deviations (IPDs) categories are defined by the study team before the first subject's initial visit and updated during the IPD reviews throughout the study prior to database lock. These definitions of IPD categories, subcategory codes, and

descriptions will be used during the course of the study. Eligibility deviations are defined in the protocol.

The number of subjects reporting Protocol Deviations and Important Protocol Deviations due to COVID-19 impact will be summarized in a table. A Protocol Deviation listing of subjects impacted due to COVID-19 impact will also be provided.

9.4 Demographic and Baseline Characteristics

All baseline tables will be summarized by the randomized treatment groups in parent study. Baseline tables will summarize the following: baseline characteristics, demographics, cardiovascular medical history, laboratory parameters, physical measurements and lipid regulating medication.

9.5 Efficacy Analyses

Table 9-1. Endpoint Summary Table

Endpoint	Primary Summary (Long-Term Safety Analysis Set and OLE Safety Analysis Set)
Primary Endpoint	
Treatment emergent adverse events 
– Adverse events– Serious adverse events– Fatal adverse events– AEs leading to withdrawal from IP– Device-related adverse events– Disease related events	Subject incidence and exposure adjusted subject incidence rate
Secondary Endpoints	
Percent change of LDL-C from baseline	Summary statistics at each scheduled visit
Achieving an LDL-C level < 40 mg/dL	Summary statistics at each scheduled visit
Exploratory Endpoints	
In subjects who completed the EBBINGHAUS study: Change from baseline in 
• SWM strategy index of executive function• SWM between-errors score• PAL total errors adjusted• RTI median 5-choice reaction time In all subjects: Change and percent change from baseline 
– non-HDL-C– ApoB– Total cholesterol– Lp(a)– Triglycerides– HDL-C– LDL-C– VLDL-C– ApoA1	Summary statistics at each scheduled visit
Subject incidence of events positively reviewed by the CEC: 
○ All deaths
■ Cardiovascular death	Subject incidence of events positively reviewed by the CEC

▪ Non-cardiovascular death▪ Undetermined Cause of death○ Cardiovascular events of interest:
▪ Myocardial Infarction (MI)▪ Coronary revascularization▪ Hospitalization for unstable angina▪ Heart failure▪ Cerebrovascular Events▪ Coronary heart disease death	
--	--

9.5.1 Analyses of Primary Endpoint

The current Medical Dictionary for Regulatory Activities version at the time of data lock will be used to code all adverse events (AEs) and disease related events to a system organ class and a preferred term.

Treatment-emergent adverse events are defined in [Section 5.3](#).

The subject incidence and exposure-adjusted subject incidence rate of all treatment-emergent adverse events, serious adverse events, fatal adverse events, adverse events leading to withdrawal of evolocumab, device-related adverse events, and disease-related events will be tabulated by system organ class (SOC), high level term (HLT), and preferred term (PT) in alphabetical order for the OLE only study period using the OLE safety analysis set. These events will also be presented by yearly subject exposure time intervals. All adverse event summaries for the primary analysis of the primary endpoint will include all treatment-emergent events reported on the Event eCRF, including CEC reviewed events and disease related events.

The analyses described above (subject incidence, exposure-adjusted subject incidence rate) will also be performed combining data from the OLE study and the parent study using the OLE safety analysis set and also be analyzed separately for the subgroup of subjects who were randomized to and received evolocumab group in the parent study with ≥ 7 years of the combined exposure for evolocumab across the **combined** parent and OLE **study**. Events from parent study classified as Target IP TEAEs will be included (adverse events occurring from the first dose of IP date to 30 days after the last dose of IP date or EOS, whichever occurs first). Disease-related events from the OLE study will be reclassified as adverse events and positively reviewed events from the OLE

study will not be included to remain consistent with parent study adverse event reporting. This analysis will be presented by the randomized treatment in the parent study.

Subject incidence of treatment emergent and serious adverse events occurring in at least 1% of the subjects by preferred term will be provided in descending order of frequency for the OLE **only** study period **and combined parent and OLE study periods.**

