5.1 Study Time Points

Baseline

The baseline value is defined as the subject's baseline value from the parent study, unless otherwise specified.

First Dose Date of Investigational Product (IP)

For each subject, the first dose date of IP is the date of the first administration of evolocumab in this OLE study.

End of Investigational Product (EOIP) Date

For each subject, end of investigational product is the date reported on End of Investigational Product Administration eCRF.

Last Dose Date of Investigational Product

For each subject, the last dose date of investigational product is defined as the date of the last administration of investigational product (evolocumab or placebo).

If the last dose was administered in-clinic, then the Last IP Dose Date is the last start date captured on the IP Administration (In-Clinic) eCRF page.

If the last dose was administered at a non-investigator site location, then the Last IP Dose Date is defined as the final dose date reported by the subject on the Non-Clinic Final Investigational Product Dose Date eCRF page.

End of Study (EOS) Date

For individual subject, the end of study date is defined as the last day that protocol-specified procedures are conducted for an individual subject, including safety follow-up and survival assessment. The EOS date is recorded on the End of Study eCRF.

Enrollment Date

The enrollment date for each subject is recorded on the Subject Enrollment eCRF **in the OLE study.**

Study Day 1

The date of the first administration of evolocumab in the OLE study or the **enrollment date** for subjects who are not administered any dose of evolocumab.

Study Day

For each subject, and for a given date of interest, study day is defined as the number of days since study day 1:

Study day = (date of interest – study day 1 date) + 1

If the date of interest is prior to the study day 1:

Study day = (date of interest – study day 1 date)

Study End Date

The study end date is the last EOS date of all enrolled subjects.

Endpoint Categories

All time-to-**first**-event endpoints in this study are categorized below.

- Composite
 - time to cardiovascular death, myocardial infarction, hospitalization for unstable angina, stroke, or coronary revascularization, whichever occurs first
 - time to cardiovascular death, myocardial infarction, or stroke, whichever occurs first
 - time to cardiovascular death or hospitalization for worsening heart failure, whichever occurs first

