 - time to ischemic fatal or non-fatal stroke or transient ischemic attack, whichever occurs first
 - time to the first fatal and non-fatal myocardial infarction
 - time to the first fatal and non-fatal stroke
- Non-mortality
 - time to the first coronary revascularization
- Mortality
 - time to cardiovascular death
 - time to coronary death
 - time to death by any cause

Censoring date

Endpoints are censored differently according to the endpoint **categories**. The censoring schema are described in below:

- censoring date for the composite and non-mortality endpoints is the EOS date in the OLE study.
- censoring (or time-to-event) for mortality endpoints are detained in appendix C.

Time-to-first-event Definition

For the time-to-first-event analysis based on combined the parent and OLE data, the events adjudicated as positive in the parent study and occurred prior to or on subject last confirmed survival status date in the parent study (i.e., primary analysis in the parent study; please see the definition in the parent study SAP version 3.1 dated Aug 09, 2016) are included in addition to the events reviewed as positive in the OLE study (defined as below).

For the time-to-first-event analysis based on the OLE data only, mortality events reviewed as positive and occurred prior to or on later of (the EOS date or last known survival status date from eCRF page(s) in this OLE study) and non-mortality events reviewed as positive and occurred prior to or on the EOS date are included.

- For those subjects who already experience such event in the parent study, their time to event and censor flag are same as those in the parent study.
- For those subjects who didn't experience such event in the parent study, the derivation of the time-to-event and censoring date is presented below

For analyses combined both the parent study and this OLE study		
Endpoint	Time-to-first-event for subjects with events	Censoring date for subjects without events
Composite or Non-mortality	First event onset date reviewed by CEC in OLE study – randomization date in the parent study +1	EOS date in OLE study
Mortality	Death endpoint date reviewed by CEC in OLE	For subjects who died not due to death endpoint, the censoring date is the death

	study – randomization date in the parent study +1	date (reviewed by CEC) in OLE study For remaining subjects, the censoring date is max (EOS date, last known survival status date from eCRF page(s)) in the OLE study

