For analyses based on OLE data only		
Composite or Non-mortality	First event onset date reviewed by CEC in OLE study – enrolment date in OLE study +1	EOS date in OLE study
Mortality	Death endpoint date reviewed by CEC in OLE study – enrolment date in OLE study +1	For subjects who died not due to death endpoint, the censoring date is the death date (reviewed by CEC) in OLE study For remaining subjects, the censoring date is max (EOS date, last known survival status date from eCRF page(s)) in the OLE study

Patient-years of follow-up for treatment emergent adverse events

For analyses based on combined both the parent study and this OLE study:

- 1) Subjects had events: date (first event) – date (first dose date in FOURIER) + 1
- 2) Subjects didn't have events: min [date (EOS in OLE), date (last dose date in OLE)+30] – date (first dose date in FOURIER) + 1

For analyses based on OLE study:

- 1) Subjects had events: date (first event in OLE) – date (first dose date in OLE) + 1
- 2) Subjects didn't have events: min [date (EOS in OLE), date (last dose date in OLE)+30] – date (first dose date in OLE) + 1

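### Supplementary combined FOURIER+OLE rates and K-M curves for death, and combined rates for AEs leading to permanent withdrawal, count FOURIER time in which members of the OLE safety set could not have the event

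*SAP*

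**What the plan says.** - **Population.** SAP 9.1 puts all analyses on the OLE safety analysis set, and SAP 6.1 limits that set to subjects with at least one open-label dose. For the combined AE tables, SAP 9.5.1 repeats that the analyses "will also be performed combining data from the OLE study and the parent study using the OLE safety analysis set". SAP section 10 records that the protocol's long-term safety set was dropped; the header of Table 9-1 still names it.
- **Entry to the OLE.** Inclusion criterion 102 requires completion of FOURIER while still on assigned product. Exclusion criterion 201 bars anyone who permanently discontinued it for any reason.
- **AE clock, combined periods.** For subjects without an event, SAP 5.1 gives patient-years as "min [date (EOS in OLE), date (last dose date in OLE)+30] – date (first dose date in FOURIER) + 1". The OLE-only version starts at first OLE dose.
- **Mortality clock, combined periods.** The SAP 5.1 table gives "Death endpoint date reviewed by CEC in OLE" and continues "study – randomization date in the parent study +1". The OLE-only version starts at OLE enrolment.
- **Outputs.** SAP 9.5.1 plans subject incidence and exposure-adjusted rates of AEs, including fatal AEs and AEs leading to withdrawal. SAP 9.5.3 plans incidence, exposure-adjusted rates and yearly K-M estimates of positively reviewed events, deaths included. Both sections cover the OLE-only and the combined periods.
- **Status.** Protocol 10.4.1 makes the OLE-only analysis primary and the combined analyses additional.

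**The concern.** Subjects are selected on what happened in FOURIER, and the clock is then started before that selection. For death and permanent withdrawal, the FOURIER segment is event-free by construction, yet it enters the patient-years and the K-M risk set. This is immortal time. The SAP text gives no delayed entry and no caveat; it also refers to Appendix C for mortality censoring, whose figure is not shown.

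Protocol 2.3 names about 7 years of total study exposure as a purpose of the extension, and the combined tables are where a reader would look for it. That reader could take the combined death and withdrawal levels as risks under long-term treatment, and they err in the favourable direction. Section 10 of the SAP discloses the change of population but not this consequence.

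**Working it through.** **1. The plan's own figure.** Two FOURIER years plus 260 weeks is 2 + 260/52 = 7.0 years, and half of 2000 subjects is 1000. This reproduces Protocol 2.3. In calendar years the OLE lasts W = 260 × 7/365.25 = 4.98.

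**2. Inputs not in the documents.** Mean FOURIER time T is not given; Protocol 3.3 says only that about 2000 of 5000 subjects have at least 2 years. I assume T = 1.5, 2 and 2.5 years. Combined AE time stops no later than 30 days after last dose, so I also use an average of W = 4 OLE years. SAP 5.1 defines no separate denominator for mortality rates, so I take the combined time-to-event clock.

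**3. Rates.** All D events fall in OLE time. The OLE-only rate is D/(N·W) and the combined rate is D/(N·(T + W)), so the combined rate is low by T/(T + W).

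| T (years) | W = 4.98 | W = 4 |
|---|---|---|
| 1.5 | 1.5/6.48 = 23% | 1.5/5.5 = 27% |
| 2 | 2/6.98 = 29% | 2/6 = 33% |
| 2.5 | 2.5/7.48 = 33% | 2.5/6.5 = 38% |

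For example, an assumed OLE death rate of 2.0 per 100 patient-years with T = 2 would appear as 2.0 × 4.98/6.98 = 1.43, or 1.41 if time also ends at the event.

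**4. K-M, one common T.** Nobody can die before T, and everyone is at risk after it. The planned and the delayed-entry risk sets are the same after T, so the curves coincide. Only the label is at fault: the curve is conditional on survival to T.

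**5. K-M, mixed T.** Assume 40% of subjects have FOURIER times uniform on 2 to 3 years and 60% uniform on 1 to 2 years. The mean is 0.4 × 2.5 + 0.6 × 1.5 = 1.9. With constant hazard h after entry:
- planned curve, from year 3 on: approximately 1 − exp(−h(t − 1.9));
- delayed-entry curve, starting at the earliest entry (year 1): 1 − exp(−h(t − 1)).

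| h per 100 PY | Year 5: planned vs delayed entry | Shortfall | Year 6.9: planned vs delayed entry | Shortfall |
|---|---|---|---|---|
| 1 | 3.05 vs 3.92% | 22% | 4.88 vs 5.73% | 15% |
| 2 | 6.01 vs 7.69% | 22% | 9.52 vs 11.13% | 14% |
| 3 | 8.88 vs 11.31% | 21% | 13.93 vs 16.22% | 14% |

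A simulation of the same mix at 2 per 100 PY gives 6.1% against 7.8% at year 5, again about 22% low.

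**6. Endpoints with a fatal component.** These include "time to cardiovascular death, myocardial infarction, or stroke, whichever occurs first", "time to the first fatal and non-fatal myocardial infarction", "time to the first fatal and non-fatal stroke" and "time to ischemic fatal or non-fatal stroke or transient ischemic attack, whichever occurs first". Only the fatal part is impossible in FOURIER time. If a share f of first events is fatal, the rate is low by f·T/(T + W): about 2 to 4% at f = 10% and 7 to 12% at f = 30% over the grid above (f is assumed).

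**7. Fatal AEs.** The denominator problem is the same, but I give no size. SAP 9.5.1 also removes positively reviewed OLE events from the combined AE tables, and Protocol 10.1.1.3 lists all deaths among the events the CEC reviews. The numerator is therefore not the OLE-only one.

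**8. Subgroup with at least 7 years of exposure.** SAP 5.3 counts exposure from first parent dose to last OLE dose plus 14 days (Q2W) or 28 days (QM), capped at EOS. A member therefore cannot have stopped before 7 years less 28 days (6.92 years) or less 14 days (6.96 years), and cannot have died before about year 7. I give no percentage: a fatal AE may start well before the death, and the 30-day follow-up and the gap between studies also matter.

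**The case against.** **The withdrawal row may not be immortal.** Exclusion criterion 201 covers only permanent discontinuation. The SAP does not say that leading to withdrawal means permanent, and the sample report form in Protocol Appendix B separates permanent discontinuation from withholding. If the parent study coded temporary stops in this row, members could have such events in FOURIER. This stands, so the sizes above apply to that row only if permanent discontinuation is what was coded. An AE that began in FOURIER and later proved fatal or led to withdrawal in the OLE is a further minor exception.

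**The K-M shortfall looks larger than it is.** A reader might compare the combined curve with a constant hazard running from year 0 and call the whole gap an error. The documents do not support that. No analysis of this set can show deaths before entry, and delayed entry does not recover them. Only the gap in step 5 can be corrected.

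**The rows are supplementary, descriptive and duplicated.** The same sections plan OLE-only results, section 10 states the population, and the 7-year aim itself concerns subjects who enrol in the OLE. This limits the impact, but it does not make the denominator right.

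**Stronger readings to resist.** A reader might infer that the primary safety analysis is biased. It is not, because OLE-only time starts at first OLE dose or at OLE enrolment. A reader might also infer a distorted comparison of randomized groups. Both groups met the same entry condition, so the defect lies mainly in absolute levels, and the plan is descriptive. Finally, dropping the long-term set is a documented choice with trade-offs, not in itself an error.

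**Conclusion.** The point holds for supplementary outputs and should be fixed. Combined exposure-adjusted rates for cardiovascular, coronary and all-cause death are low by 23 to 38% over the assumed range of FOURIER and OLE times. The same applies to AEs leading to permanent withdrawal, subject to how the parent study coded them. The direction does not depend on the assumptions, since any positive FOURIER time lowers the rate.

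The correctable K-M error for death runs from nil with one common FOURIER time to about 22% at year 5 and 15% at year 6.9 under the assumed mix and hazards of 1 to 3 per 100 patient-years. Combined fatal AEs share the fault, at a size not stated. Endpoints with a fatal component are affected to a smaller degree. OLE-only analyses, crude n/N percentages and purely non-fatal combined rows are not affected. The hidden Appendix C figure could add detail on censoring, but the SAP 5.1 table already fixes the combined mortality origin at FOURIER randomization.

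**What to change.** Add to SAP 5.1, for the combined periods: for cardiovascular, coronary and all-cause death, subjects enter the risk set and patient-years at OLE enrolment; for fatal AEs and AEs leading to permanent withdrawal of IP, they enter at first OLE dose; earlier time is not counted. Alternatively, report the OLE-only results in place of these combined rows.

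In either case:
- label the K-M and the remaining combined results, including endpoints with a fatal component, as conditional on completing FOURIER on assigned product;
- state whether AEs leading to withdrawal means permanent discontinuation in both studies;
- do not present fatal-AE or withdrawal rates as risks in the subgroup with at least 7 years of exposure;
- state whether CEC-reviewed OLE deaths are kept in the combined fatal-AE row, or drop that row.

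The cost is SAP wording and a changed start date for a few rows, on data already held. The downside is that these rows then add little beyond the OLE-only tables, and the reported rates become less favourable.

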4. SUBJECT ELIGIBILITY

4.1 Inclusion and Exclusion Criteria

4.1.1 Inclusion Criteria

- 101 Subject has provided informed consent before initiation of any study-specific activities/procedures.
- 102 Subject has completed FOURIER (Study 20110118) while still receiving assigned investigational product.

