4.1.2 Exclusion Criteria

- 201 Investigational product was permanently discontinued during FOURIER for any reason, including an adverse event or serious adverse event.
- 202 Subject is currently receiving treatment in another investigational device or drug study, or ended treatment on another investigational device or drug study(ies) within less than 4 weeks. Other investigational procedures while participating in this study are excluded.
- 203 Subject is not likely to be available to complete protocol-required study visits or procedures and/or to comply with required study procedures to the best of the subject's and investigator's knowledge.

204 Subject has a history or evidence of any other clinically significant disorder, condition, or disease that, in the opinion of the investigator or Amgen physician, if consulted, would pose a risk to subject safety or interfere with the study evaluation, procedures, or completion.

205 Subject has a known sensitivity to any of the active substances or excipients (eg, sodium acetate) to be administered during dosing.

206 Female subject is pregnant or breastfeeding or is planning to become pregnant or planning to breastfeed during treatment with evolocumab and within 15 weeks after the end of treatment with evolocumab.

207 Female subjects of childbearing potential who are not willing to use an acceptable method(s) of effective birth control during treatment with evolocumab and for an additional 15 weeks after the end of treatment with evolocumab are excluded.

Female subjects of non-childbearing potential are not required to use contraception during the study and include those who have had a hysterectomy, bilateral salpingectomy, bilateral oophorectomy, or who are postmenopausal. Postmenopausal is defined as 12 months of spontaneous and continuous amenorrhea in a woman \geq 55 years old; or age $<$ 55 years but no spontaneous menses for at least 2 years; or age $<$ 55 years and spontaneous menses within the past 1 year, but currently amenorrheic (eg, spontaneous or secondary to hysterectomy), and with postmenopausal gonadotropin levels (luteinizing hormone and follicle-stimulating hormone [FSH] levels $>$ 40 IU/L), postmenopausal estradiol levels ($<$ 5 ng/dL), or according to the definition of postmenopausal range for the laboratory involved.

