6.2.2 Dosage Adjustments, Delays, Rules for Withholding or Restarting, Permanent Discontinuation

No dose adjustments of evolocumab will be allowed in this study.

If, in the opinion of the investigator, a subject is unable to tolerate evolocumab, that subject will discontinue evolocumab but should continue to return for all other study procedures and measurements until the EOS.

The decision to rechallenge the subject after therapy changes should be discussed and agreed unanimously by the subject, investigator, and Amgen. If signs or symptoms recur with rechallenge of evolocumab, then evolocumab should be permanently discontinued.

Stopping and rechallenge rules due to hepatotoxicity are provided in [Section 6.4](#).

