Statistical Analysis Plan

Protocol Title:	A Multicenter, Open-label, Single-arm, Extension Study to Assess Long-term Safety of Evolocumab Therapy in Patients with Clinically Evident Cardiovascular Disease	
Short Protocol Title:	FOURIER-OLE	
Protocol Number:	20130295	
NCT Number:	NCT02867813	
Authors:	[REDACTED] [REDACTED] (PAREXEL), [REDACTED] (PAREXEL)	
Sponsor:	Amgen Inc. [name] [name] [contact]	
SAP Date:	Document Version	Date
	Original (v1.0)	10 June 2019
	Amendment 1 (v2.0)	21 December 2021
	Amendment 2 (v3.0)	08 March 2022

Version Number	Date (DDMMYYYY)	Summary of Changes, including rationale for changes
Original (v1.0)	10JUN2019	
Amendment 1 (v2.0)	21 DEC 2021	
Changes
 
1. Change one of the authors from [REDACTED] and then author added [REDACTED] [REDACTED] Rationale: Study lead statistician role had been transitioned to [REDACTED]. Study lead transition role transitioned from [REDACTED] to [REDACTED]. Study Statistician role also transition from [REDACTED]2. Update statistical analysis plan (SAP) version and date throughout this SAP Rationale: Statistical analysis plan was amended3. Removed long-term safety analysis set and related analysis from SAP and clarified the rationale in section 10. Rationale: The pre-specified planned analyses in the SAP focus on the long term safety data in the subjects who enrolled into this OLE study (i.e., OLE safety analysis set) rather than the long-term safety analysis set which also includes FOURIER subjects who did not rollover into this OLE study. We will include FOURIER data and OLE data from those that enrolled in the OLE for the analysis. More details will be provided in SAP section 9.4. Add the explanations for "ABI" and "PAD" in the list of abbreviations Rationale: To explain the abbreviation of a new definition added in section 5.25. Added explanation for "K-M" in the list of abbreviations as included for efficacy tables.6. Added new subgroup analysis in the list per request from Clinical team to analyze the long term exposure effect in subjects with evolocumab.7. Update the definition of planned covariates in section 4.1 Rationale: Since this study is for

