4.2 Subgroups

The planned subgroups include the following:

- Baseline age (< 65 years, ≥ 65 years; < 75 years, ≥ 75 years)
- Sex (male, female)
- Race (white, non-white)
- Prior non-hemorrhagic stroke (yes, no)
- Symptomatic PAD (yes, no)
- Prior MI (No, < 1 year, 1 - < 2 years, ≥ 2 years)
- Baseline PCSK9 level (< median, ≥ median)
- Baseline LDL-C by quartiles (Q1, median, Q3)
- Baseline HDL-C by quartiles (Q1, median, Q3)
- Baseline triglycerides by quartiles (Q1, median, Q3)
- Baseline hsCRP (< 2 mg/L, ≥ 2 mg/L)
- Ezetimibe use at baseline (yes, no)
- ACC/AHA high statin background therapy intensity at baseline (yes, no)
- History of type 2 diabetes (yes, no)
- Heterozygous Familial Hypercholesterolemia (HeFH) at OLE enrollment (definite, probable, neither definite nor probable)
- **Subjects who were randomized to and received evolocumab group in the parent (i.e., FOURIER) study with ≥ 7 years of the combined exposure for evolocumab across the parent study and this OLE study**

5. Definitions

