5.3 Other Study Related Definitions

Treatment-Emergent Adverse Event (TEAE)

Events are categorized as Adverse Events (AEs) or **Disease-related Events (DREs)** starting on or after first dose of investigational product as determined by the flag indicating if the event started prior to the first dose on the Events eCRF and up to the EOS/Safety Follow-up visit or 30 days after the last administration of evolocumab, whichever is earlier.

Treatment-Emergent Disease-Related Events

Events categorized as Disease-related Events defined in Protocol Section 9.1.1 starting on or after first dose of investigational product as determined by the flag indicating if the disease-related event started prior to the first dose on the Events eCRF and up to the EOS/Safety Follow-up visit or 30 days after the last administration of evolocumab, whichever is earlier.

Analytical Study Week Assignments

Analytical windows will be used to assign parameters to study weeks. The algorithm is provided in Appendix A.

Investigational Product (IP)

Investigational product includes evolocumab 140 mg every two weeks (Q2W) and 420 mg monthly (QM).

IP Exposure Period in Months (For OLE period)

For subjects whose last IP dose is Q2W:

IP exposure period in OLE period= $[\min(\text{last IP dose date in OLE period} + 14 \text{ days, EOS date}) - \text{first IP dose date in OLE period} + 1] / 365.25 \times 12$

For subjects whose last IP dose is QM:

IP exposure period in OLE period= $[\min(\text{last IP dose date in OLE period} + 28 \text{ days, EOS date}) - \text{first IP dose date in OLE period} + 1] / 365.25 \times 12$

IP Exposure Period in Months (For combined the parent and OLE periods)

For subjects whose last IP dose is Q2W:

IP exposure period in combined periods= $[\min(\text{last IP dose date in OLE period} + 14 \text{ days, EOS date in OLE period}) - \text{first IP dose date in the parent period} + 1] / 365.25 \times 12$

For subjects whose last IP dose is QM:

IP exposure period in combined periods= $[\min(\text{last IP dose date in OLE period} + 28 \text{ days, EOS date in OLE period}) - \text{first IP dose date in the parent period} + 1] / 365.25 \times 12$

Study Exposure Period in Months (For OLE period)

For each subject, study exposure period in OLE period = $[(\text{EOS date} - \text{enrollment date}) + 1] / 365.25 \times 12$

Study Exposure Period in Months (For combined the parent and OLE periods)

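### In the ≥ 7-year exposure subgroup, the rate of AEs leading to withdrawal is biased strongly downward, because staying on evolocumab to about year 7 is the entry rule

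*SAP*

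**What the plan says.** SAP 4.2 lists a subgroup of subjects randomized to and treated with evolocumab in FOURIER, "with ≥ 7 years of the combined exposure for evolocumab across the parent study and this OLE study". The SAP version history says it was added "to analyze the long term exposure effect in subjects with evolocumab". SAP 9.5.1 applies it to the primary endpoint: subject incidence and exposure-adjusted rates on combined FOURIER and OLE data are also produced for the "subgroup of subjects who were randomized to and received evolocumab group in the parent study with ≥ 7 years" of combined exposure. One of the repeated rows is AEs leading to withdrawal of evolocumab.

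Three other rules matter:

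- **Exposure.** SAP 5.3 counts combined IP exposure from the "first IP dose date in the parent period" to the last OLE dose plus 14 days (Q2W) or 28 days (QM), capped at the OLE end-of-study date. Treatment gaps are not subtracted.
- **Person-time.** For combined analyses, SAP 5.1 starts the clock at "date (first dose date in FOURIER) + 1". It stops at the first event or, without one, at the earlier of end of study and 30 days after the last OLE dose.
- **OLE entry.** Protocol 4.1.1 requires that "Subject has completed FOURIER (Study 20110118) while still receiving assigned investigational product". Protocol 4.1.2 excludes anyone for whom "Investigational product was permanently discontinued during FOURIER for any reason".

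**The concern.** The subgroup is chosen on something known only at the end: whether the subject was still taking evolocumab at about year 7. That is almost the complement of the outcome in the withdrawal row. A permanent stop before that point removes both the subject and the event. The FOURIER years are already free of permanent stops because of the OLE entry rules. An AE that ended treatment can count only if the last dose came near or after year 7, whatever the onset date of the AE, yet each member contributes about 7 years of person-time.

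Tolerability is part of the primary objective. Protocol 2.3 gives 7-year safety and tolerability as the reason for enrolling the longer-exposed subjects. The withdrawal row is the direct tolerability measure in the table built for that purpose, and a reader could take a near-zero rate as evidence of 7-year tolerability.

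The same selection acts on fatal AEs. That row is not quantified here. It may be nearly empty for all subjects anyway, since the combined analysis drops positively reviewed OLE events and all deaths go to the CEC. Other AE rows are not quantified either.

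**Working it through.** **The plan's own figure.** Protocol 2.3: 2000 × 50% = 1000 subjects; 2 years + 1820/365.25 = 6.98, about 7 years. This reproduces, and it includes no attrition.

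**Inputs from the documents.** OLE length T = 260 weeks = 1820 days = 4.983 years. Dosing credit c = 14 or 28 days. Follow-up tail = 30 days = 0.082 years. Threshold = 7 years.

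**Assumed, because the documents do not give them.** F, the years from first FOURIER dose to OLE day 1; a, the OLE hazard of AE withdrawal; b, the hazard of other stops and death; h = a + b. Hazards are constant in the OLE, and permanent stops are zero in FOURIER by the entry rules. The range is h = 2, 5, 10% per year with a/h = 10, 20, 50%.

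**Who can qualify.** The last dose must fall at or after 7 × 365.25 − 1 − c days from the first FOURIER dose, which is year 6.96 (Q2W) or 6.92 (QM). With a last dose at week 260, F must be at least 1.976 (Q2W) or 1.938 (QM) years. If the last dose is one interval earlier, F must be at least 2.014 years.

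**Formulas**

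- All parent-evolocumab OLE subjects with the same F: incidence e = (a/h)(1 − exp(−hT)); person-years per subject PY = F + (1 − exp(−hT))/h + 0.082(1 − e).
- Subgroup: window in which a stop can be seen, w = F + T + c − 7; incidence es = (a/h)(1 − exp(−hw)); PYs = (7 − c) + (1 − exp(−hw))/h + 0.082(1 − es).

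**Example: a = 1%, b = 4%, F = 2.5, QM**

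- Unselected: (1 − exp(−0.05 × 4.983))/0.05 = 4.411; e = 4.41%; PY = 2.5 + 4.411 + 0.078 = 6.989; rate = 0.631 per 100 PY.
- Subgroup: w = 0.560 years (204 days); (1 − exp(−0.05 × 0.560))/0.05 = 0.552; es = 0.55%; PYs = 6.923 + 0.552 + 0.082 = 7.557; rate = 0.073 per 100 PY.
- Ratio = 0.073/0.631 = 11.6% (10.8% for Q2W).

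**Range over all assumed hazards**

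| F (years) | Window w, Q2W / QM (days) | Subgroup rate as % of unselected, Q2W | Same, QM |
|---|---|---|---|
| 2.05 | 26 / 40 | 1.4-1.5 | 2.2-2.4 |
| 2.25 | 99 / 113 | 5.5-5.8 | 6.3-6.6 |
| 2.5 | 190 / 204 | 10.6-11.1 | 11.4-11.9 |
| 3.0 | 373 / 387 | 20.7-21.6 | 21.5-22.4 |
| 3.5 | 556 / 570 | 30.8-31.9 | 31.5-32.7 |

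F drives the ratio; the hazards hardly move it. A simulation with discrete doses (4 million subjects, a = 1%, b = 4%) gives 0.8/1.6, 5.7/6.4, 10.4/11.0, 20.6/20.6 and 30.7/31.3% for Q2W/QM. It agrees closely from F = 2.25 upward. At F = 2.05 the simulated ratio is clearly lower, so the formula understates the bias there.

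**Choice of reference.** The unselected combined rate is itself diluted by FOURIER years in which no permanent stop could occur. Counted from OLE day 1, the example's rate is 4.41%/(6.989 − 2.5) = 0.98 per 100 PY, and the subgroup shows 0.073/0.98 = 7.4% of it.

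**Can the row detect worse tolerability?** Raise a from 1% to 4% per year and keep the rest of the example. The subgroup then shows 0.29 per 100 PY, less than half of the 0.63 seen without selection at a = 1%.

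**Stop and restart.** Protocol 6.2.2 allows for restarting: "The decision to rechallenge the subject after therapy changes should be discussed and agreed unanimously". As gaps are not subtracted, such subjects can stay in the subgroup. If 0, 5, 10 or 20% of AE withdrawals are followed by a restart, the example's ratio is about 12, 16, 21 or 30%.

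**Secondary: the count of 1000.** 1000 × (1 − x)^5 = 904, 774, 590 for assumed losses x = 2, 5, 10% per year.

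**The case against.** - **Another definition exists.** The subgroup text cites no exposure formula, and SAP 5.3 also defines a study exposure period that runs to end of study regardless of dosing. Under that definition a subject who stops evolocumab and stays in follow-up would remain in the subgroup, and this bias would not arise. The wording, exposure for evolocumab in subjects who received it, points to the IP formula. The missing cross-reference is a real gap, and the SAP should close it.
- **It is one row of a supplementary descriptive table.** This is true, and no test is affected. The OLE-only analysis, the combined analysis in the full OLE safety set, the discontinuation table in SAP 9.2 and the Kaplan-Meier death estimates in SAP 9.5.3 are not conditioned on 7 years. SAP 9.5.1 already plans OLE-only yearly intervals. That limits the weight of the point but does not correct the row. With no inference planned, the tabulated rates are the result.
- **Describing people who reached 7 years is legitimate.** For some questions it is. For withdrawal it is close to circular, and the stated purpose is the effect of long exposure. No placebo subject could have 7 years of evolocumab, so the lack of a comparator is no error in itself, but nothing beside the row reveals the selection.
- **The size rests on assumptions.** This stands. The direction does not depend on them.
- **Five full years of attrition is near the worst case.** This stands too. At F = 2.5 (QM) only 4.42 OLE years are needed, which gives about 915, 797 or 627.

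**Conclusion.** The concern holds, with high confidence in the direction, on the reading that the subgroup uses the SAP 5.3 IP exposure period. The subgroup rate of AEs leading to withdrawal would be roughly 1-33% of the rate in comparable unselected subjects for FOURIER times of 2.05 to 3.5 years, and about 12% in the worked example at 2.5 years. These sizes rest on assumed FOURIER time, constant stopping hazards and no restarts. Restarts after as many as 20% of AE withdrawals would still leave the example at about 30%. The point should be fixed, but its scope is narrow: it concerns the ≥ 7-year table and not the primary OLE-only analysis. The protocol's figure of about 1000 subjects is a ceiling before attrition, which is a minor separate matter.

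**What to change.** 1. State in SAP 4.2 and 9.5.1 which SAP 5.3 exposure definition applies.
2. Define the long-exposure safety group by facts known at OLE entry: randomized to and dosed with evolocumab, with at least 2 years of FOURIER exposure. Since about 1.94-2.01 years are needed to reach 7, this covers essentially everyone who could.
3. Report AE, SAE and withdrawal rates in that group by year of cumulative exposure, with all subjects at risk at the start of each interval in the denominator. Count withdrawal person-time from OLE day 1.
4. Keep ≥ 7 years only as an exposure count, with reasons for not reaching it.
5. State whether CEC-reviewed deaths enter the combined fatal row. If they do not, refer to the Kaplan-Meier estimates for mortality.
6. In Protocol 2.3, describe the 1000 as an upper figure before attrition.

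The minimum alternative to steps 2-4 is to omit the withdrawal row from the ≥ 7-year table and refer to the OLE-only withdrawal row by parent arm.

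The cost is SAP wording and minor programming, with no new data. Fewer subjects will contribute to the latest exposure intervals, and the headline count will be smaller.
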